PUSH PLUS PROTEIN PILOT STUDY FOR HIP FRACTURE PATIENTS
PROTOCOL (Version 3.0)

Summary of Modifications to Protocol Version 2.0 for Version 3.0

Version (date)	Section	Brief Summary of Modification
9-5-2018	10.1 and 10.2	We removed the Biodex ankle plantarflexion-dorsiflexion measurement from the baseline and 16-week follow-up assessments. We will test Biodex knee flexion/extension only, which is the best representative marker for torque/ power production and importantly related to gait and mobility function. The Biodex ankle test is less reliable and the knee test a better performance predictor. When investigators looked at data from the CAP-MP companion study, they learned that many in this functionally very challenged cohort could not achieve the 60 deg/sec needed to perform the ankle test; thus, the torque/power was not calculated, as there was more missing data for the Biodex ankle test than for the Biodex knee test which was more complete. The ankle test for the selected contraction velocity is more difficult for many in this study population to achieve in order to capture valid measurement. Therefore, experts in the Department of Physical Therapy and Rehabilitation Science (PTRS) suggest using the Biodex knee test only for the current pilot study because it more accurately represents the entire subject cohort being tested. Participants will be able to correctly perform the knee test which was not true for the ankle test in the companion study.
	10.1 and 10.2	We added the Four-Square Step Test (FSST) to be done at the baseline and 16-week follow-up visits as a dynamic balance assessment.

Summary of Modifications to Protocol Version 1.0 for Version 2.0

Version (date)	Section	Brief Summary of Modification
7-24-2018	All sections	Changed study clinician to study physician
	12.5 and Figures 5b-d	Modified procedures for reportable adverse events to coincide with reporting procedures outlined by NIA and the Pepper Center OAIC.
	7.5	Modified recruitment procedures to describe how patients will be contacted after discharge from the hospital and how potential participants who contact the study office will undergo a brief pre-screening to assess eligibility.
	17	Modified the publication policy to state that publications will be overseen by study leadership and added a note that final papers using CAP or CAP-MP data may need to be reviewed by the CAP PASC.

PUSH Plus Protein Pilot Study for Hip Fracture Patients

Principal Investigator:

[name]

Information Technology	IT	Skilled nursing facility	SNF
Informed Consent Form	ICF	Spine Patient Outcomes Research Trial	SPORT
Institutional Review Board	IRB	Standard Operating Procedure	SOP
Investigational Drug Services	IDS	Statistical Analysis Software	SAS
Intervention Monitor	IM	Systolic blood pressure	SBP
Manual of Procedures	MOP	University of Maryland Baltimore	UMB
		Weighted estimating equations	WEE

Section 1: Executive Summary

Hip fracture is a common problem among older individuals. This year in the United States approximately 260,000 people aged 65 and older will break a hip. The goal of current standard of care after hip fracture is to achieve independent, household ambulation 2-3 months after surgery, yet decreased functional ability typically persists well beyond three months and many patients never resume independent ambulation outside the home. Previous research has established that one must be able to walk at least 300 meters (~330 yards) within 6 minutes to re-establish routine interactions in the community, such as going to the store or to church. In part, this is based on the average distance from handicapped parking spaces into most facilities. Activity and exercise are believed to be of benefit for reducing disability in older adults, yet the majority of older adults does not participate in regular exercise and is not active. This is especially true for older adults following hip fracture after they complete the usual rehabilitation program.

This research study is being done to test a 16-week, multi-part exercise intervention for hip fracture patients that will be supervised by specially trained physical therapists (PTs). The exercise intervention uses a novel machine to provide strength and endurance training in the home. This has been shown in smaller studies to be safe and effective at increasing strength. We want to test whether adding a protein supplement to the exercise intervention leads to more improvements in a person's ability to walk in their own home and in the local community. With this knowledge, we hope to help a greater number of hip fracture patients enjoy a more complete recovery and improved overall health.

The research is based on the premise that successful community ambulation requires certain factors that are influenced by underlying physical or chemical processes. The key factors include endurance, walking speed, muscle strength, balance, lower extremity function, skeletal integrity, and fracture healing. We believe that physical activity and protein supplementation can impact these factors to improve the ability to walk. We want to gain a better understanding of which factors play a role by performing tests that measure physical function, strength, balance, level of inflammation, bone turnover rate, muscle density, and body composition.

Participant data from this pilot study will be compared to data from participants who received the PUSH intervention without protein in two recently completed studies: 1) Community Ambulation Project (CAP parent study) and 2) Community Ambulation Project- Mechanistic Pathways (CAP-MP ancillary study).

Study Title

PUSH Plus Protein Pilot Study for Hip Fracture Patients (hereafter referred to as PUSH Plus Protein)

Objectives

The primary outcome will be to test whether the PUSH Plus Protein intervention improves community ambulation (as measured by distance walked in six minutes) compared to PUSH intervention alone (from CAP study) at the end of 16 weeks. The effects of PUSH Plus Protein on precursors to community ambulation compared to the PUSH intervention alone (CAP study) and the effects of PUSH Plus Protein intervention on the mechanistic factors compared to PUSH intervention alone (from CAP-MP study) will also be examined. In addition, the safety and tolerability of delivering the PUSH Plus Protein intervention to hip fracture patients will be assessed.

Design and Outcomes

In addition to providing important information on adherence, feasibility, and safety, this pilot study of 30 hip fracture patients has the unique advantage of being able to compare data to two recently completed studies where participants received the PUSH intervention without protein supplementation described below.

Participants in this pilot will receive the same specific multi-component 16-week intervention, PUSH, as participants in the multi-site CAP randomized controlled trial. The PUSH intervention uses a novel machine to provide strength and endurance training in the home. The purpose of this pilot study is to test whether adding a protein supplement to the PUSH intervention leads to greater improvement in a person's functional ability compared to the PUSH intervention alone; therefore, data in this pilot study will be compared to data from participants in the CAP study across the three clinical sites who received the PUSH intervention alone (n=105). Our working hypothesis is that PUSH Plus Protein will lead to greater improvements in ability to walk in the community compared to PUSH measured using the distance walked in six minutes (SMWT).

We will also compare the effect of PUSH Plus Protein intervention to PUSH intervention alone on secondary outcomes in the CAP study believed to be precursors to community ambulation including activities of daily living (ADLs), quality of life, lower extremity physical performance, increase of ≥ 50 meters in distance walked in six minutes, cognitive status, and nutritional status.

We can also compare participants in the pilot study to participants who received PUSH alone in the CAP-MP study (HP-53145) (n=19) to examine whether PUSH Plus Protein has an impact on the mechanistic factors on the pathway to recovery of ambulatory ability after hip fracture. We will assess whether, at the end of the 16 week intervention, participants in the PUSH Plus Protein intervention, compared to PUSH alone, have: a) greater muscle volume and attenuation (i.e., reduced intra-muscular fat) of the thigh; b) greater lower extremity strength; c) better gait parameters; d) greater bone mineral density and bone strength; e) more bone formation and less bone resorption; and f) lower levels of circulating inflammatory cytokines.

The pilot study will provide important information related to the safety and tolerability of delivering the PUSH Plus Protein intervention to hip fracture patients. We will also be able to estimate the sample size requirements for a more definitive study.

Study activities for participants meeting eligibility criteria will take place after post-acute rehabilitation ends, up to 26 weeks after admission to the hospital for hip fracture. Patients age 60 and older who have had surgical repair for hip fracture will be identified in study hospitals or by self-referral and evaluated for eligibility. Following consent to participate, eligible participants will undergo a comprehensive baseline assessment. Participants completing the required measures of the baseline assessment will be eligible to receive the intervention. All participants will receive the PUSH Plus Protein intervention. The follow-up assessment will occur after the intervention is completed, approximately 16 weeks after baseline testing.

Interventions and Duration

All participants will receive the PUSH Plus Protein intervention. Within a week of completing baseline testing, the study physical therapist (PT) will initiate the exercise intervention and the protein supplement in the home setting. Participants will receive two physical therapy visits a week for 16 weeks, on non-consecutive days, for a total of 32 visits. Each visit will last

approximately 60 minutes. Visits will take place in the participant's place of residence. At the same time, participants will receive a daily whey-based protein powder supplement containing 27.6g of protein. Participants will also receive 2,000 IU of vitamin D3, 600 mg of calcium, and a multivitamin daily during the 16-week study period and counseling with a registered dietitian to ensure body weight stability and adequate nutrient intake inclusive of a healthy diet.

PUSH Exercise Intervention

The PUSH exercise intervention is based on improving specific precursors to community ambulation. The intervention addresses endurance with continuous upright exercise for 20 minutes; function by improving fast walking needed to navigate streets outdoors, standing from a chair, and stair negotiation; muscle performance by exercising to enhance lower extremity strength in functionally relevant muscles moving through locomotion-appropriate movements and ranges; and balance by performing unilateral activities and activities with decreased base of support. The components of exercise are woven together into one program that minimizes participant burden. Participants will be instructed to complete the endurance component independently one to two times/week by walking for a similar duration and intensity as they have been doing with the PT during the supervised visits.

The strength components of the muscle performance intervention will be performed using a portable progressive resistive exercise device (Shuttle® MiniPress, Contemporary Design Company, [name]). Muscle performance will focus on bilateral hip extensors, hip abductors, knee extensors, and plantar flexors because of their role in function, specifically gait and transfer activities. Balance and strength will be addressed with additional exercises performed while standing. The endurance intervention will begin initially with two to three minutes of continuous upper and lower extremity active range of motion (AROM) with the participant sitting. These exercises are intended to increase the participants' heart rate (HR) or exertion closer to the target zone. The participant will then be asked to walk on level surfaces and up and down a single or multiple steps, if able and available, to keep the HR within the training zone for 20 minutes. The PT may also engage the participant in additional exercises such as upper and lower extremity AROM exercises to keep the HR elevated.

As a measure of treatment fidelity, we will monitor physiologic response (heart rate) during the intervention sessions by measuring heart rate. Heart rate monitoring will provide a dichotomous variable reflecting whether, during each segment of the intervention session, the participant's average HR was equal to or greater than his or her target heart rate (± 5 beats).

Protein Supplement

Participants will receive a whey-based protein powder supplement containing 27.6g of protein. This dose induces maximum muscle protein synthesis post-exercise. Participants will mix the supplement in 8 oz. of water (or other beverage) or soft food (e.g., yogurt, soup) and consume immediately following each exercise session with the study PT. On days when they do not have a physical therapy visit with the study PT, participants will be instructed to take the supplement at the meal time closest to the time of scheduled PT visits to maintain regular daily dosing schedule.

Nutrition Intervention

Given the importance of maintaining nutrition in older adults after an acute event, we will provide all participants with 2000 IU vitamin D3, 600 mg of calcium, and a multivitamin daily for the duration of the 16-week study. Nutritional counseling will also be provided to ensure weight stability, adequate nutrient intake of 1.2-1.5 g protein/kg body weight inclusive of a healthy diet (50% carbohydrate, 20% protein, 30% fat). Participants will be screened at the time of baseline

testing to assess nutritional risk using the Mini Nutritional Assessment-Short Form (MNA®-SF). Those who score ≤7 (malnourished) on the MNA®-SF at baseline and participants with serum albumin 2.5-3.5 g/dl (regardless of the score on MNA®-SF) will receive a visit from a registered dietitian (RD) in their place of residence within seven days of baseline testing. The RD will evaluate and counsel them on making dietary modifications based on their protein, caloric and other dietary deficiencies using a standardized approach across the three study sites. The RD will follow up with participants by telephone one week after the visit to assess understanding and implementation of recommendations. Participants who score 8-11 (at risk of malnutrition) on MNA®-SF at baseline and have serum albumin level >3.5 g/dl will receive a telephone dietary consultation with the RD within seven days of baseline testing. Based on the participant's eating habits and food intake, the RD may make the clinical determination that an in-person consultation is warranted. In these cases, the RD will schedule an in-person dietary consultation, following the same protocol as those who score in the malnourished range. Those screening in the normal range (with a score ≥12 on the MNA®-SF) at baseline and who have serum albumin level >3.5 g/dl will receive brief telephone contact within seven days of baseline testing from the RD to discuss the importance of calorie and protein intake. Weight will be monitored during home PT visits every four weeks and those who lose 2% or more body weight in a four-week period will receive another telephone consultation by the study RD. This protocol applies to anyone who loses 2% or more of body weight, regardless of whether the participant is trying to lose weight. In the event that a weight measurement is not obtained at the last PT visit, the participant's weight at the 16-week follow-up assessment will be compared to his or her baseline weight and, if there is weight loss of 5% or more, the study physician will review the participant's weight trajectory, baseline BMI, baseline MNA®-SF score, and registered dietitian's documentation and, if warranted based on clinical judgment, will refer the participant to a dietitian or medical provider for follow-up of possible poor nutritional status.

Sample Size and Population

The target sample size for this pilot study is 30 hip fracture patients who will receive the PUSH Plus Protein intervention. Study inclusion criteria are: 1) Closed, non-pathologic, minimal trauma hip fracture with surgical fixation; 2) Age 60 or older at time of baseline testing; 3) Living in the community at time of fracture and at time of baseline testing; and 4) Ambulating without human assistance during the two months prior to fracture. Participants for whom it is not safe to participate in the intervention will be excluded, as will those who are very unlikely to benefit and in whom the intervention is not feasible.

Section 2: Clinical Site

University of Maryland Baltimore
[name]
Principal Investigator
[name]
[name]
[contact]
[contact]
[contact]

Section 3: Study Organization

The PUSH Plus Protein Pilot study is a single-site study conducted at the University of Maryland Baltimore. In addition to the Department of Epidemiology and Public Health (EPH) where the PI has a faculty appointment, the project will utilize resources provided by the Department of Physical Therapy and Rehabilitation Science (PTRS), University of Maryland General Clinical Research Center (GCRC), University of Maryland Investigational Drug Service (IDS), Baltimore Veteran's Affairs Maryland Health Care System (VAMHCS), and the University of Maryland Claude D. Pepper Older American Independence Center (UM-OAIC) Data and Safety Monitoring Board (DSMB). Please see Section 18: for a complete Study Team Roster.

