8.1 Overview

Participants will receive two physical therapy visits a week, on non-consecutive days, for a total of 32 visits and be given a whey-based protein supplement containing 27.6g of protein daily for 16 weeks. Each visit will last approximately 60 minutes. Participants will also receive 2,000 IU of vitamin D3, 600 mg of calcium, and a multivitamin daily during the 16-week study period and counseling with a registered dietitian to ensure body weight stability and adequate nutrient intake inclusive of a healthy diet. Missed visits can be replaced during subsequent weeks if there is at least one day in between visits and no more than three visits in the week. Visits will take place in the participant's place of residence.

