8.2 Nutritional Support

Given the importance of ensuring adequate nutrition to those who receive the intervention, we will provide all participants with 2000 IU of vitamin D3, 600 mg of calcium, and a multivitamin daily for the duration of the 16-week study and nutritional counseling to ensure weight stability, adequate nutrient intake of 1 g protein/kg body weight inclusive of a healthy diet (50% carbohydrate, 20% protein, 30% fat). Participants will be screened at the time of baseline testing to assess nutritional risk using the Mini Nutritional Assessment-Short Form (MNA®-SF).¹¹⁷ Those who score ≤ 7 (malnourished) at baseline and participants with serum albumin 2.5-3.5 g/dl (regardless of the score on MNA®-SF) will receive a visit from a registered dietitian (RD) in their place of residence within seven days of baseline testing. The RD will evaluate and counsel them on making dietary modifications based on their protein, caloric and other dietary deficiencies using a standardized approach across the three study sites.¹¹⁸⁻¹²⁰ The RD will follow up with participants by telephone one week after the visit to assess understanding and implementation of recommendations. Participants who score 8-11 (at risk of malnutrition) at baseline and have serum albumin level >3.5 g/dl will receive a telephone dietary consultation with the RD within seven days of baseline testing. Based on the participant's eating habits and food intake, the RD may make the clinical determination that an in-person consultation is warranted. In these cases, the RD will schedule an in-person dietary consultation, following the same protocol as those who score in the malnourished range. Those with a score ≥ 12 on the MNA®-SF and who have serum albumin level >3.5 g/dl at baseline will receive brief telephone contact within seven days of baseline testing from the RD to discuss the importance of calorie

and protein intake. Weight will be monitored during home PT visits every four weeks and those who lose 2% or more body weight in a four-week period will receive another telephone consultation by the study RD. This protocol applies to anyone who loses 2% or more of body weight, regardless of whether the participant is trying to lose weight. Vitamin D, calcium, and multivitamin adherence will be reviewed by the PT every four weeks (by pill counts) and assessed by self-report every four weeks by telephone interview.

[figure not shown]

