11.1.2 Safety Considerations for Study Assessments

All study assessments will be done by certified staff who will be trained to perform the tests safely. If, during the SMWT or the SPPB a participant reports chest pain, tightness or pressure, significant shortness of breath or difficulty breathing, or feeling faint, lightheaded, or dizzy, the test will be stopped. If the participant weighs more than 400 pounds or if s/he is unable to lie supine, the whole body and hip DXA scans will not be done. Participants with prior hardware in the non-fractured hip will not have a hip DXA scan. If a participant is unable to lie supine or be left alone in a room, the thigh CT scan will not be done. Participants unable to put full weight on the fractured side or unable to stand for 30 seconds without an assistive device will not perform the GAITrite or Biodex measures. All research staff who come in contact with study participants will be CPR certified and will be trained to provide immediate care when faced with medical emergencies. Also, institutional and community emergency medical services will be activated if needed.

Table 2 describes a summary of safety alerts and the appropriate action during clinical assessments.

Table 2. Safety Alerts and Actions for Study Assessments

ALERT	ACTION
Resting blood pressure SBP > 145mm Hg or DBP > 90mm Hg	Qualified staff will inform the participant if noted on more than one occasion.
Resting blood pressure SBP > 170mm Hg or SBP < 90mm Hg or DBP > 100mm Hg or DBP < 50mm Hg	Qualified staff will encourage the participant to seek additional follow-up and/or medical evaluation. Physical performance testing will be deferred until consultation with the study physician.
Resting blood pressure or after SMWT SBP > 185mm Hg or SBP < 90mm Hg or DBP > 110mm Hg or DBP < 50mm Hg	Qualified staff will consult with the study physician and follow up as needed.
Resting pulse Rate > 120 or < 40 beats/min	Qualified staff will consult with the study physician and follow up as needed.

Table 2. Safety Alerts and Actions for Study Assessments

Chest pain, dizziness, significant shortness of breath, or severe musculoskeletal pain during the intervention or study assessment.	Qualified staff will consult with the study physician and follow up as needed.
MNA®-SF Score \leq 7 at the follow-up assessment	Qualified staff will talk to the participant and provide a referral for additional follow-up and/or medical evaluation for possible malnutrition.

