Weight loss \geq 2% body weight in four weeks during intervention period	Participant will be referred to the registered dietician for follow-up by telephone.
Participant expresses desire to commit suicide	Call primary care provider and report findings. Report to study coordinator/study physician for follow-up and clearance.

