11.1.8 Safety Measures for Nutritional Support

If a participant loses 2% or more body weight in a four-week period, the participant will be referred to the registered dietician for follow-up by telephone.

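### Physician review of a 5% weight loss by week 16 applies only when the last PT weight is missing, so gradual loss in a fully weighed participant can pass 5% with no weight-loss alert

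*Protocol*

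**What the plan says.** The protocol has two weight-loss rules.

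- **Rate rule.** Section 8.2 says "those who lose 2% or more body weight in a four-week period will receive another telephone consultation by the study RD". The Executive Summary has the same rule, Section 11.1.8 repeats it ("If a participant loses 2% or more body weight in a four-week period"), and the action in Table 2 (Section 11.1.2) is "Participant will be referred to the registered dietician for follow-up by telephone".
- **Cumulative rule.** This appears only in the Executive Summary, under Nutrition Intervention. It begins "In the event that a weight measurement is not obtained at the last PT visit". The 16-week clinic weight is then compared with baseline and "if there is weight loss of 5% or more, the study physician will review" the weight trajectory, baseline BMI, baseline MNA-SF and dietitian notes. The physician, "if warranted based on clinical judgment, will refer the participant to a dietitian or medical provider", so the action is discretionary.

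PTs weigh participants every four weeks (Section 9.6.2). Clinic weight is scheduled for everyone at baseline and follow-up (Sections 9.5.3 and 10.2). Table 2 also has a nutrition alert at follow-up: for an MNA-SF score of 7 or lower, staff "provide a referral for additional follow-up and/or medical evaluation for possible malnutrition".

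**The concern.** The cumulative rule works as a fallback for a missed weigh-in, yet it measures something the rate rule does not: total loss since baseline. No section available to us makes that comparison when the last PT weight was obtained. Two participants with the same gradual 6% loss are then handled differently. The one who missed the last weigh-in goes to the physician; the one with a complete weight record, whose trajectory would be the more informative, does not. A participant who loses 2% or more in several periods gets several dietitian calls, but no weight-loss rule takes that person to the physician, whatever the total.

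Section 11.1.7 describes these patients as often at risk of protein and calorie malnutrition, and Section 8.2 makes weight stability an aim of the counselling. What is at stake is whether a loss the protocol already treats as worth a physician's attention is looked at.

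**Working it through.** The plan states no figure to reproduce. The check asks how much weight can be lost without meeting the rate rule.

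**Inputs from the protocol:** a 2% threshold per four-week period; a 5% cumulative threshold; weighing every four weeks for 16 weeks. This gives four intervals if the baseline weight starts the first one, or three if only PT weights are compared with each other. The protocol does not say which.

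**Steady loss per interval that reaches 5%**
- Four intervals: 1 − 0.95^(1/4) = 1.27%
- Three intervals: 1 − 0.95^(1/3) = 1.70%

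**Largest total with every interval below 2%**
- Four intervals: 1 − 0.98^4 = 7.76%, so just under 7.8%
- Three intervals: 1 − 0.98^3 = 5.88%, so just under 5.9%. This counts only loss inside the three compared intervals.

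**Examples with no trigger**
- Even loss, assumed 70 kg start, 1.5% per interval: 70.0, 68.95, 67.92, 66.90, 65.89 kg, a 5.9% loss.
- Uneven loss of 1.9%, 1.5%, 1.0%, 0.7%: 1 − 0.981 × 0.985 × 0.990 × 0.993 = 5.01%.

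**Allowing for weighing error.** The documents give no loss rate, loss pattern or weighing error, so everything here is assumed: independent normal error with SD 0.25%, 0.5% or 1% of body weight; the total log-loss split evenly or by a symmetric Dirichlet distribution with parameter 10 (mildly), 3 (moderately) or 1 (very uneven); 400,000 draws per case.

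Chance of no 2% trigger, four intervals, at SD 0.25% / 0.5% / 1%:

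| Loss pattern | True 5% loss | True 6% loss |
|---|---|---|
| Even | 93% / 48% / 15% | 67% / 23% / 7% |
| Mildly uneven | 72% / 40% / 14% | 32% / 16% / 6% |
| Moderately uneven | 42% / 28% / 12% | 12% / 9% / 5% |
| Very uneven | 16% / 14% / 8% | 3% / 3% / 3% |

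Over three intervals the ranges are 4–48% (true 5% loss) and 0.1–4% (true 6% loss).

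**What the fix would newly catch.** This needs both no 2% trigger and a measured week-16 loss of 5% or more, treating the week-16 PT and clinic weights as one:

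| Intervals | True 5% loss | True 6% loss |
|---|---|---|
| Four | about 1–45% | about 1–66% |
| Three | about 0.2–15% | about 0.1–2% |

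Over four intervals, the upper ends need perfectly even loss and the smallest error. With uneven loss and 0.5% error, the four-interval yield is about 4–14% (true 5%) and 3–14% (true 6%). These counts leave out participants who met the 2% rule and would gain physician review in addition to their dietitian calls.

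**The case against.** The strongest reply is that this is an optional refinement. The 5% rule stands in for a final 2% check that could not be made, and a fully weighed participant has no lost check to replace. The rate rule acts during treatment, when a dietitian can still help, and any four-interval loss of about 7.8% or more must trigger it. The added review would come after the intervention, is discretionary, and ends in a referral to a dietitian or medical provider. Everyone has dietitian contact at baseline, and Section 8.1 provides close contact afterwards: "Participants will receive two physical therapy visits a week, on non-consecutive days". The MNA-SF is given at the same follow-up visit. With 30 participants and no base rate, the number affected could be near zero. Operational detail sits in a Manual of Procedures that is not available here (Sections 13 and 15.4.1) and may say more.

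Most of this stands, and it keeps the point minor. It does not close the gap. The MNA-SF referral depends on a score, not on weight loss as such; baseline dietitian contact comes before the loss; and no cumulative check is stated for PT visits. The Executive Summary does say that the protocol covers anyone losing 2% or more, but that sentence follows the four-week rule and explains that intent to lose weight is irrelevant. Sections 8.2 and 11.1.8 and Table 2 all tie the trigger to four weeks.

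A reader might infer that the plan contradicts itself, or that fully weighed participants go unmonitored whatever their condition. Neither is supported. A fallback rule beside a rate rule is consistent, and these participants are screened against the 2% threshold every four weeks.

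**Conclusion.** The point holds as a minor participant-safety improvement. A participant weighed at every PT visit can lose 5.0% to just under 7.8% of body weight over four intervals, or just under 5.9% over three, with no weight-loss alert. Repeated losses of 2% lead to dietitian calls with no stated physician review. Those bounds follow from the thresholds alone.

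How often this would happen is unknown. The simulated percentages are conditional on a true loss of 5% or 6% and on assumed error and pattern, and the three-interval yields are much smaller than the four-interval ones. A reader might take the 93% or 66% as the share of participants who would be missed; the documents give no basis for that. Confidence is medium, because the Manual of Procedures could contain a wider rule. The primary analysis and sample size are unaffected.

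**What to change.** In the Executive Summary, under Nutrition Intervention, delete the clause "In the event that a weight measurement is not obtained at the last PT visit". Every participant's 16-week weight is then compared with baseline, and a loss of 5% or more goes to the discretionary physician review already described. Repeat the rule in Sections 8.2 and 11.1.8 and in Table 2.

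No new measurement is needed, since both clinic weights are already scheduled. The cost is at most 30 extra chart reviews by the study physician, plus a minor protocol modification that must be approved by the UMB IRB before it goes to the study hospitals' IRBs (Section 16.1). The change acts only at week 16 and does not detect gradual loss any earlier.
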